9.4.5. Other Safety Analyses

Safety measures will include AEs, vital signs, and treatment exposure. Events that are newly reported after the first dose of IP used or reported to worsen in severity from baseline (details will be described in SAP) will be considered TEAEs.

Analyses of AEs will be descriptive and include all data collected during the treatment period. AEs during the lead-in period and the safety follow-up period will be provided in a listing.

Serious AEs, AEs reported as the reason for discontinuation from the IP or study, and TEAEs will be summarized in tables using the Medical Dictionary for Regulatory Activities (MedDRA) Preferred Term sorted by decreasing frequency. Treatment-emergent AEs will also be summarized by preferred term sorted by decreasing frequency within the SOC for all TEAEs and by maximum severity. For events that are gender-specific (as defined by MedDRA), the denominator and computation of the percentage will include only patients from the given gender. The number and proportion of patients with at least 1 event for each type of event will also be summarized.

In addition, time in hypoglycemic ranges will be assessed by CGM analyses.

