To evaluate total daily, basal, and prandial insulin dose with LY900014 treatment and degludec	Prandial: TDD ratio for the maintenance period
Tertiary/Exploratory	
To evaluate the safety of LY900014	Adverse events and vital signs
To explore the relationship between 
 • ICR and TDD • ISF and TDD • ICR and ISF with LY900014 treatment	
 • Slope of the linear regression line of ICR or ISF on the reciprocal of TDD • Slope of the linear regression line of ICR on ISF, for the maintenance period
To explore ISF with LY900014 treatment	ISF at the end of the maintenance period
To explore glucose profiles, obtained from CGM use with LY900014 treatment	Actual and change from baseline in mean sensor glucose with CGM use during the maintenance period
To explore highest PPG level within 4 hours* after meal(s), obtained from CGM use, with LY900014 treatment	Actual and change from baseline in highest PPG level within 4 hours after meal(s), with CGM use during the maintenance period

Objectives	Endpoints
To explore the time from start of meal to highest PPG level within 4 hours* after meal(s), obtained from CGM use, with LY900014 treatment	Actual and change from baseline in minutes from start of meal to highest PPG level within 4 hours after meal(s), with CGM use during the maintenance period
To explore the percentage of time spent in hypoglycemic glucose ranges, obtained from CGM use, with LY900014 treatment	Actual and change from baseline in percentage of time with sensor glucose values <54 mg/dL, with CGM use during the maintenance period
To explore percentage of time spent in hyperglycemic glucose ranges, obtained from CGM use, with LY900014 treatment	Actual and change from baseline in percentage of time with sensor glucose values >250 mg/dL, with CGM use during the maintenance period
To explore within-day glucose variability, obtained from CGM use, with LY900014 treatment	Actual and change from baseline in within-day CV of sensor glucose, with CGM use during the maintenance period
To explore proportion of participants achieving CGM-based glycemic targets, with LY900014 treatment	
The proportion of participants with percentage of time in
 
 • target glucose range, 70-180 mg/dL, >70% • hypoglycemia, <54 mg/dL, <1% • hyperglycemia, >250 mg/dL, <5%, 
with CGM use during the maintenance period

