5.2. Determination of Sample Size

Approximately 34 participants will be assigned to study treatment such that 30 evaluable participants will complete the maintenance period, assuming a 10% dropout rate.

The study is not strictly powered to demonstrate a statistically significant change from baseline in the primary endpoint (percentage of time with glucose within 70 to 180 mg/dL) because of the exploratory nature of the study.

Using a standard deviation of 12%, the sample will provide approximately 80% coverage probability that the half-width of the 95% confidence interval (CI) of the change from baseline in the primary endpoint falls within 4.93%.

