6.1. General Considerations

Statistical analysis of this study will be the responsibility of Lilly or its designee. Any change to the data analysis methods described in the protocol will require an amendment ONLY if it changes a principal feature of the protocol. Any other change to the data analysis methods described in the protocol, and the justification for making the change, will be described in the SAP or the clinical study report. Additional exploratory analyses of data will be conducted, as deemed appropriate.

The following populations are defined in [Table ITSZ.6.1](#).

Table ITSZ.6.1. Patient Populations

Population	Description
Entered	All participants who give informed consent
Enrolled	All participants who continue the study after Visit 2
Treated	All assigned participants who receive at least 1 dose of the assigned study treatment after Visit 3

Unless otherwise specified, all efficacy and safety analyses will be conducted on the Treated Population. Unless otherwise noted, all tests will be conducted at a 2-sided alpha level of 0.05, and CIs will be calculated at 95%, 2-sided. Comparison between baseline and endpoints will be performed at the full significance level of 0.05. No multiplicity adjustment will be made.

The definitions of baseline and post-baseline for the safety and efficacy analyses depend on which analysis period is being used. The following analysis periods will be used:

- Lead-in Period – from Day -11 to Day -1
- Treatment Period – from first dose to Day 46 (Visit 14) while on investigational product (IP) and from first dose to Day 46 (Visit 14) including all data regardless of IP use
- Treatment Period and Safety Follow-up Period – from first dose to Visit 801 including all data regardless of IP use

[Table ITSZ.6.2](#) describes the rules for determining the patient population, baseline, and postbaseline observations for the different analysis periods.

The data on IP is defined based on the following rules:

- for data only measured at an office visit (eg, HbA1c and 1,5 Anhydroglucitol [1,5-AG]), if the office visit date (or laboratory sample collection date) is within 14 days of the date of last study drug dose of the current treatment period (treatment period), then postbaseline data measured at or prior to that office visit will be considered as data on IP for the current treatment period (treatment period).

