The proportion of patients who have achieved the guidance (Battelino 2019) recommended CGM targets of glycemic control (Table ITSZ.6.6) during the lead in period (baseline) and the maintenance period (endpoint) will be summarized.

Table ITSZ.6.6. Guidance Recommended CGM Targets of Glycemic Control

Percentage of time with sensor glucose (24-hour)	Guidance Recommendation
target range	
70-180 mg/d.L (3.9-10.0 mmol/L, both inclusive)	>70%
hypoglycemia range	
<54 mg/dL (3.0 mmol/L)	<1%
hyperglycemia range	
>250 mg/dL (13.9 mmol/L)	<5%

Other than that, all continuous variables (actual and change from baseline, if applicable) will be analyzed by using the ANCOVA defined in Section 6.1.

In addition, the following standardized glucose summary reports from the ambulatory glucose profile (AGP) will be generated, based upon all the observed CGM data during the lead in period and the maintenance period, regardless of whether they are collected on valid CGM days:

- 24-hour period at individual patient level
- 24-hour period at the treatment level
- 0 to 4 hours relative to meal starting time, excluding data collected after the next meal event (if any is captured within the interval) at the treatment level
- 0 to 4 hours relative to meal starting time, by meal (breakfast, lunch, and dinner) and by infusion set wear day excluding data collected after the next meal event

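### The single-group ANCOVA interval for mean time below 54 mg/dL is too narrow: its standard error omits baseline variation, and any right skew makes it worse

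*SAP*

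**What the plan says.** After the glycemic-target proportions, SAP 6.13 states that all other continuous CGM variables "will be analyzed by using the ANCOVA defined in Section 6.1". Table ITSZ.6.5 places time below 54, from 54 to 69, and below 70 mg/dL in a hypoglycemia safety category. Table ITSZ.4.1 lists the first of these as exploratory: "Actual and change from baseline in percentage of time with sensor glucose values <54 mg/dL, with CGM use during the maintenance period".

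The ANCOVA in SAP 6.1 has one group and one covariate, baseline. SAP 6.3 restricts it to completers. On numbers, SAP 5.2 says: "Approximately 34 participants will be assigned to study treatment such that 30 evaluable participants will complete the maintenance period, assuming a 10% dropout rate". On inference, SAP 6.1 says: "all tests will be conducted at a 2-sided alpha level of 0.05, and CIs will be calculated at 95%, 2-sided". LS means and standard errors are to be shown for both level and change. No transformation, rank method or bootstrap is given for a variable that departs from normality.

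Protocol 9.4.5 adds that "time in hypoglycemic ranges will be assessed by CGM analyses". Protocol 8.2.6 excuses level 1 and level 2 events from AE reporting because CGM data will cover them.

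Other planned outputs bear on the same question:
- mean, SD, median, minimum and maximum (SAP 6.1);
- the proportion of participants with less than 1% of time below 54 mg/dL at baseline and endpoint (SAP 6.13);
- rate and incidence of severe hypoglycemia (Table ITSZ.6.4).

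**The concern.** The study asks whether prandial dosing can be more aggressive without more late post-meal hypoglycemia (Protocol 2.1 and 4.3). Only severe events are collected as AEs, so CGM time in the low ranges is the main quantitative evidence on that question. The ANCOVA is the only formal inference planned for it.

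Two features make its interval doubtful. First, in a single group the LS mean at the observed mean baseline is simply the raw mean, yet its standard error is built from the residual variance. Second, a percentage with a 1% target sits close to zero (1% of 288 daily readings is 2.88 readings), so right skew is plausible. An interval that is too narrow, and that misses mostly on the low side, could make hypoglycemia look lower or better determined than it is.

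**Working it through.** **The plan's own precision figure.** SAP 5.2 states: "Using a standard deviation of 12%, the sample will provide approximately 80% coverage probability" for the half-width "of the change from baseline in the primary endpoint falls within 4.93" percentage points. With n = 30 and SD = 12, the half-width reached with 80% probability is t(0.975, 29) × SD × √[χ²(0.80, 29)/29/30] = 2.045 × 12 × √(35.14/29/30) = 4.93. Inflating 30 for 10% dropout gives 30/0.9 = 33.3, so 34. Both figures reproduce. They rest on a one-sample t interval for change, not on the ANCOVA standard error, and they concern the primary endpoint. Neither document gives a mean, SD, skewness or share of zeros for time below 54 mg/dL.

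**Standard error, with no assumption about skew.** Let the SDs at baseline and endpoint be s1 and s2, and their correlation r. I assume that the LS mean is evaluated at the observed mean baseline.
- The ANCOVA variance for level and for change is s2²(1 − r²)/n.
- The true variance of the mean level is s2²/n, so the ratio is k = 1 − r².
- The true variance of the mean change is (s1² + s2² − 2r·s1·s2)/n. With equal SDs, k = (1 + r)/2.
- Large-sample coverage is 2Φ(1.96√k) − 1.

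| r (equal SDs) | k, level | coverage | k, change | coverage |
|---|---|---|---|---|
| 0 | 1.00 | 95% | 0.50 | 83% |
| 0.5 | 0.75 | 91% | 0.75 | 91% |
| 0.7 | 0.51 | 84% | 0.85 | 93% |

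Simulation with normal data, n = 30 and r = 0.5 gives 91.4% for both, with balanced misses.

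**Adding skew, which is an assumption.** The simulations used n = 30 and 40,000 trials per scenario, with gamma or lognormal positive values, baseline mean 0.5%, zeros in 0-60% of participants, CV of positive values 1.0-1.5 and latent correlation 0-0.7. Coverage of the endpoint mean was 80-90%. The interval lay wholly below the truth in 8.5-18% of trials and wholly above it in 0.3-4%. A separate set of simulations gave 81-92%, with 7-17% low. The shortfall appears even with no zeros.

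For change, lognormal with 30% zeros and CV 1.2:

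| Endpoint mean ÷ baseline mean | latent correlation | ANCOVA coverage | wholly below / above truth | paired t coverage |
|---|---|---|---|---|
| 1.0 | 0 | 80.2% | 16.1% / 3.7% | 95.8% |
| 1.0 | 0.7 | 86.6% | 10.9% / 2.6% | 95.9% |
| 1.5 | 0.5 | 88.0% | 11.1% / 0.9% | 93.7% |
| 2.0 | 0.5 | 88.7% | 10.5% / 0.8% | 91.6% |
| 0.5 | 0.5 | 62.3% | 19.7% / 17.9% | 91.6% |

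The formula explains the last row. In that scenario the observed correlation is 0.39 and the SD halves with the mean. Then k = 0.25 × (1 − 0.39²)/(1 + 0.25 − 0.39) = 0.212/0.86 = 0.246, and coverage is 2Φ(1.96 × 0.496) − 1 = 67% before any skew. At a ratio of 1.5, k = 2.25 × 0.848/(1 + 2.25 − 1.17) = 0.917, which gives 94%. The rest of the loss in that row comes from skew.

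**Replacement for the level.** Bootstrap-t against ANCOVA, endpoint mean, with 3,000 trials and 800 resamples:

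| Distribution | bootstrap-t coverage | ANCOVA coverage | median width, bootstrap-t / ANCOVA (percentage points) |
|---|---|---|---|
| Gamma, 20% zeros, CV 1.0 | 94.9% | 90.1% | 0.47 / 0.38 |
| Gamma, 40% zeros, CV 1.5 | 94.5% | 85.7% | 0.91 / 0.61 |
| Lognormal, 30% zeros, CV 1.2 | 92.9% | 85.7% | 0.54 / 0.42 |

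A percentile bootstrap helps little (88-92%).

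**The case against.** The strongest defence is that, under the model's assumptions, the ANCOVA interval is an exact 95% interval conditional on the observed baselines. That is true, and the shortfall above concerns the population mean. The SAP does not say it wants the conditional quantity, and its own precision calculation uses the unconditional one.

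A reader might infer that a large share of zeros and heavy skew invalidate normal-theory methods here. The documents do not support that. They give no distribution for this variable. The participant value averages all valid CGM days (SAP Appendix 1, 9.2), so a 24-hour zero needs no reading below 54 mg/dL over about 10 days. The paired t interval is also normal-theory, yet it covers 95-97% on the same skewed data when the mean is unchanged.

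A reader might also infer that the interval always understates hypoglycemia. That holds for the endpoint level under skew, and for change when the mean is unchanged or rises. It fails when time below 54 mg/dL halves, where misses are about equal on both sides.

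Finally, the measure is exploratory, no decision rule uses its interval, and medians, the proportion under 1% and severe-hypoglycemia summaries are already planned. These limit the consequence. They do not supply a valid interval for the mean: SAP 6.1 rules out formal comparison of categorical measures, and severe events answer a different question.

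**Conclusion.** The point holds in a limited form. The planned interval for mean time below 54 mg/dL is too narrow as an interval for the population mean.

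- The standard-error part needs no distributional assumption beyond evaluation at the observed mean baseline. It costs about 4 percentage points of coverage at correlation 0.5 with equal SDs. It applies equally to the other variables analysed by this ANCOVA, including the primary endpoint.
- The skew part is conditional on an assumed right-skewed distribution. Under it, coverage is about 80-92% for the endpoint mean, with about 7-18% of intervals wholly below the truth. For an unchanged or rising change it is about 80-91%. For a halved mean it is about 60-65%, without a clear direction.

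The change is worth making because it is cheap and concerns the main evidence on non-severe hypoglycemia. It is not critical, given the exploratory status and the descriptive outputs already planned.

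**What to change.** In SAP 6.13, exempt the time-in-hypoglycemia variables (below 54, 54-69 and below 70 mg/dL) from the ANCOVA interval, and specify:

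- **Change:** mean paired change with a 95% paired t interval. Coverage in the scenarios tried is about 94-97% if the mean is unchanged or rises by up to half, about 92% if it doubles, and about 90-94% if it halves.
- **Endpoint level:** mean with a studentized bootstrap interval, resampling participants, with the number of resamples and the seed fixed in advance. Add the IQR to the median already planned. Coverage is about 90-95%, which is better than ANCOVA but not always nominal.
- **Rank test:** if a Wilcoxon signed-rank result is wanted, label it supplementary, since it tests a different quantity from the mean change, and state how zero differences are handled.

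Keep the proportion under 1% and the severe-hypoglycemia summaries as they are. The simulations were set up for time below 54 mg/dL only; for the other two ranges the case rests on the standard-error argument. The cost is SAP wording, minor programming and wider intervals: in the three bootstrap scenarios the median width rose from 0.38-0.61 to 0.47-0.91 percentage points.

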6.14. Clinical Trial Registry Analyses

Additional analyses will be performed for the purpose of fulfilling the Clinical Trial Registry (CTR) requirements.

Analyses provided for the CTR requirements include the following:

- Summary of AEs, provided as a dataset which will be converted to an XML file. Both SAEs and ‘Other’ Non-SAEs are summarized by MedDRA PT.
- An AE is considered ‘Serious’ whether or not it is a TEAE.
- An AE is considered in the ‘Other’ category if it is both a TEAE and is not serious. For each Serious AE and ‘Other’ AE, for each term and treatment, the following are provided:
 - the number of participants at risk of an event
 - the number of participants who experienced each event term
 - the number of events experienced.
- For each SAE, these additional terms are provided for EudraCT:
 - the total number of occurrences causally related to treatment
 - the total number of deaths
 - the total number of deaths causally related to treatment.
- Consistent with www.ClinicalTrials.gov requirements, ‘Other’ AEs that occur in fewer than 5% of patients/subjects in every treatment may be excluded if a 5% threshold is chosen. Allowable thresholds include 0% (all events), 1%, 2%, 3%, 4%, and 5%.

- AE reporting is consistent with other document disclosures for example, the CSR, manuscripts, and so forth.

7. Unblinding Plan

Not applicable as this is an open label study.

8. References

- Baghurst PA. Calculating the mean amplitude of glycemic excursion from continuous glucose monitoring data: an automated algorithm. *Diabetes Technol Ther.* 2011;13(3):296-302.
- Clarke W, Kovatchev B. Statistical tools to analyze continuous glucose monitor data. *Diabetes Technol Ther.*
- Hirsch IB. Glycemic variability: It's not just about A1c anymore! *Diabetes Technol Ther.* 2005;7(5):780-783.

Appendix 1. Derivation of CGM Variables

9.1. General Derivation Specifications

All CGM outcome variables will only be analyzed for each patient at Visit 3 (baseline) and Visit 14 (endpoint) based upon the CGM data collected from valid CGM days, excluding data (if any) that are collected while patients are temporarily off Humalog during the lead-in period or temporarily off IP during the maintenance period. A valid CGM day to be counted into the calculation for a visit must have at least 70% of the total measures that are supposed to be obtained (Section 6.13).

No missing CGM values will be imputed.

Since the CGM values may not be measured at the exact same time for each day for a specific individual patient, due to device changes or gaps in usage, non-overlapping intervals ('buckets') of 5 minutes over 00:00:00 to 23:59:59 (00:00:00 to 00:04:59, 00:05:00 to 00:09:59, etc.) will be used for any derivations requiring time-matched measurements across days within a visit.

All CGM parameters will be estimated to precision of 1 decimal place, unless stated otherwise. All CGM glucose derivations will be conducted in units of mg/dL and mmol/L.

Only readings collected from valid CGM days while patients are on Humalog in the lead-in period or on IP during the treatment period, will be included in the derived.

9.2. Glucose in Target Ranges, Hypoglycemia or Hyperglycemia

Glucose in target range, hypoglycemia or hyperglycemia will be calculated as the average value of percentage of time within a glucose range (target, hypo- or hyperglycemia ranges) on all valid CGM days during that visit.

The percentage of time within a glucose range (target, hypo- or hyperglycemia ranges) will be calculated as the number of observations within the specified range divided by the number of observations in the time interval (eg, 24-hour period). The duration (in minutes) within the glucose range will then be calculated as the percentage of time within the glucose range times the length of the period (24 hour, 18 hour, and 6 hour, for the periods of 24-hour, daytime or nighttime, respectively).

For example, if a patient had a total of 15 observations with glucose values <70 mg/dL (3.9 mmol/L) out of a total of 288 observations recorded during the 24-hour period in a valid CGM day at Visit 3, the percentage of time spent in hypoglycemia during the 24-hour period for this patient at that valid CGM day at Visit 3 will be calculated as $15/288 = 5.2\%$. The duration (in minutes) with hypoglycemia (glucose value <70 mg/dL [3.9 mmol/L]) during the 24-hour period for this patient at that valid CGM day at Visit 3 will be calculated as the percentage times 1440, (ie, $15/288 * 1440 = 75.0$ minutes). Then derive the CGM outcome for each visit by averaging across all valid CGM days at that visit.

The percentage and duration in ranges within 0 to 1 hour, 0 to 2 hours, 0 to 3 hours, and 0 to 4 hours after meals will also be derived.

9.3. Incremental Area under the Glucose Curve (iAUC)

iAUC_{0-T} will be calculated as the average value of iAUC on all valid CGM days during that visit with sufficient data to calculate the iAUC_{0-T} (Section 6.13). For each day, iAUC_{0-T} will be calculated as the sum of areas of all individual trapezoids within the time frame according to the formula:

$$iAUC_{0-T} = \sum_{i=1}^k A_i = \sum_{i=1}^k \frac{(G_i - G_0) + (G_{i-1} - G_0)}{2} \Delta t_i$$

where A_i is area of the respective trapezoid, G_i is glucose concentration at a particular time, G_0 is the starting glucose concentration before the start of the meal, Δt_i is the time interval between consecutive CGM values, which should be always 5 minutes unless missing data occur, and k is the total number of intervals within the time frame 0-T. If the intermediate time points are missing, the next available time point will be used in calculating the trapezoid area. Also since it is possible that $G_i < G_0$ or $G_{i-1} < G_0$, A_i could also be negative. G_0 , the starting glucose concentration, will be calculated as the average of the CGM values in the time window [-19, 0] mins relative to the start of the meal (at most 3 CGM values); G_k , the last glucose concentration, is defined as the average of the CGM values in the window [0, +14] minutes relative to the last time point of the time frame (at most 2 CGM values). For example, to calculate iAUC_{0-2hr} after the start of breakfast, G_k will be the average of the CGM values in the window [0, +14] minutes relative to the 2 hours after the start of breakfast. The derivation of each iAUC_{0-T} will require that G_0 and G_k values are both available. The derivation iAUC_{0-T} on a specific infusion set wear day, requires that time 0 and time T fall on the same infusion set wear day, but it is acceptable that the CGM measures in the window [-19,0] for G_0 and [0+14] for G_T fall on the previous or the next infusion set wear day.

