Efficacy Endpoint: Hyperglycemia					
	Duration (in minutes) and percentage of time with glucose values >180, 181-250 and >250 mg/dL [10.0, 10.1-13.9 and 13.9 mmol/L]	X	X	X	
Efficacy Endpoint: Daily CGM Data Summary					
	Mean sensor glucose	X	X	X	
	Median sensor glucose	X	X	X	
Efficacy Endpoint: Glucose Variability and Risk Assessment					
Within-Day	CV	X	X	X	
	SD	X	X	X	
	IQR	X	X	X	
Between-Day	CV	X	X	X	
	SD	X	X	X	
Overall ^e	CV	X	X	X	
	SD	X	X	X	
	IQR	X	X	X	

Efficacy Endpoint: Highest Postprandial Glucose					
	Time from start of meal to the highest postprandial glucose level (minutes) within 4 hours after meal(s)				X
	Highest postprandial glucose level within 4 hours after meal(s)				X
	Highest postprandial glucose excursion level within 4 hours after meal(s)				X
Safety Endpoint: Hypoglycemia ^f					
	Duration (in minutes) and percentage of time with sensor glucose values <54, 54-69 and <70 mg/dL [3.0, 3.0-3.8 and 3.9 mmol/L]	X	X	X	X

Abbreviations: AUC = area under curve; CGM = continuous glucose monitoring; CV = coefficient of variation; hr = hour; IQR = interquartile range; SD = Standard deviation.

- ^a Daytime: 0600 hours to midnight (06:00:00-23:59:59 on the 24-hour clock).
- ^b Nighttime: midnight to 0600 hours (00:00:00-05:59:59 on the 24-hour clock).
- ^c By meals: for morning (breakfast), midday (lunch) and evening (dinner) meals and overall (average across all meals). The start time of morning, midday and evening meals are determined as the first entry in the CGM data during [04:00:00, 11:00:00], (11:00:00, 15:00:00] and [17:00:00, 21:00:00], respectively. When calculating time in ranges (target, hypo, hyper) for meals (0 to 1 hour, 0 to 2 hours, 0 to 3 hours and 0 to 4 hours), any data that are collected after the next meal event will be excluded.
- ^d Mean sensor glucose measured at different time points (1, 2, 3 or 4 hours) after the start of the meal minus mean sensor glucose at the start of meal
- ^e Overall variability refers to the variability calculated based upon all the CGM measurements collected across all valid days for each derivation period
- ^f In addition, postprandial hypoglycemia during the following time interval after each meal and overall will also be derived: 0 to 1 hour, 0 to 2 hours, 2 to 4 hours, 0 to 4 hours. The calculation will exclude the data from patients who have had the next meal event before the end of time interval.

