9.4. Mean Sensor Glucose Excursions

Mean sensor glucose excursions in a postmeal time interval (0-1 hr, 0-2 hr, 0-3 hr or 0-4 hr) will be calculated by averaging all excursion values within the time interval. Excursions will be derived by subtracting glucose values by the starting glucose concentration, which is the average of the CGM values in the time window [-19, 0] mins relative to the start of the meal (at most 3 interstitial glucose measures).

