9.8.2. Highest Postprandial Glucose Level within 4 hours after Meals

Highest postprandial glucose level excursions within 4 hours after meals, will be calculated as the maximum glucose value during 0 to 4 hours after start of meal, excluding the data from patients who have had the next meal event.

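### The SAP derives post-meal iAUC and mean glucose excursion without a next-meal rule, so breakfast and some lunch values can include the response to the following meal (minor; exploratory outcomes only)

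*SAP*

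**What the plan says.** SAP 6.13 (Table ITSZ.6.5) lists iAUC and mean sensor glucose excursion by meal, each over 0-1, 0-2, 0-3 and 0-4 h. It analyses continuous CGM variables, actual and change from baseline, by ANCOVA.

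- **iAUC (SAP 9.3).** For each day it is "calculated as the sum of areas of all individual trapezoids within the time frame according to the formula". The starting and final glucose are needed (the derivation requires that the "values are both available"), and individual areas "could also be negative", so the result is a net area.
- **Mean excursion (SAP 9.4).** It "will be calculated by averaging all excursion values within the time interval". Footnote d of the table describes it instead by time point ("Mean sensor glucose measured at different time points (1, 2, 3 or 4 hours) after the start of the meal", less the value at meal start). Neither text mentions a following meal.
- **Other post-meal outputs.** These do deal with a following meal. Footnote c says that "any data that are collected after the next meal event will be excluded", but that sentence opens "When calculating time in ranges (target, hypo, hyper) for meals", which limits it to time in ranges. Footnote f has an exclusion for postprandial hypoglycemia. SAP 9.8.1 and 9.8.2 derive time to highest PPG and its level "excluding the data from patients who have had the next meal event". The 0-4 h ambulatory glucose profile (AGP) reports in 6.13 drop readings after the next meal.

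**The concern.** If lunch starts three hours after breakfast, the breakfast 0-4 h window holds an hour of lunch response. As written, 9.3 and 9.4 credit that hour to breakfast. Highest PPG for the same breakfast is handled under a next-meal exclusion, so two descriptions of one meal would rest on different data.

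The titration scheme is built around post-meal glucose, so a reader will look to the by-meal results to see how each prandial dose performed. A breakfast value that includes part of the lunch response does not measure the breakfast dose. If meals were spaced differently in the lead-in and maintenance periods, that difference would also appear as a change in iAUC or excursion.

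**Working it through.** **Step 1. Which outputs carry a next-meal rule?**

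| Post-meal output | Place in SAP | Next-meal rule |
|---|---|---|
| Time in ranges | Table ITSZ.6.5, footnote c | Yes, later readings dropped |
| Postprandial hypoglycemia | footnote f | Yes, excluded |
| Time to highest PPG | 9.8.1 | Yes, excluded |
| Highest PPG | 9.8.2 | Yes, excluded |
| 0-4 h AGP reports | 6.13 | Yes, later readings dropped |
| iAUC 0-T | 9.3 | None |
| Mean excursion 0-T | 9.4, footnote d | None |

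No general rule in 6.13 or 9.1 reaches the last two rows. The 70% data-sufficiency criterion counts readings and does not detect a second meal.

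**Step 2. Can meals overlap under the SAP's windows?** Footnote c places breakfast at 04:00-11:00, lunch after 11:00 to 15:00, and dinner at 17:00-21:00. The smallest gaps are:

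- breakfast to lunch: 11:00 to just after 11:00, so just over 0 h;
- lunch to dinner: 17:00 − 15:00 = 2 h;
- dinner to next breakfast: 24 + 4 − 21 = 7 h.

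So breakfast values at any T can be affected, although the short windows need a late breakfast and an early lunch. Lunch can be affected at 0-3 h and 0-4 h. Dinner cannot reach the next main meal. The average across meals inherits whatever breakfast and lunch contain.

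**Step 3. Size for one meal (illustrative).** The plan gives no figure for these outcomes, no curve and no meal spacing. Assume each meal adds a rise r(t) = P·(t/p)·exp(1 − t/p), with peak height P at time p, and that rises from successive meals add. The area up to time s is P·e·p·F(s/p), where F(x) = 1 − (1 + x)e^(−x). With an identical next meal at gap g, the overstatement of iAUC 0-T is F((T − g)/p) / F(T/p), and P cancels.

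For T = 4 h:

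| Next meal at | p = 1.25 h, F(3.2) = 0.829 | p = 1.0 h, F(4) = 0.908 |
|---|---|---|
| 3.5 h | 0.062/0.829 = 7% | 0.090/0.908 = 10% |
| 3.0 h | 0.191/0.829 = 23% | 0.264/0.908 = 29% |
| 2.5 h | 0.337/0.829 = 41% | 0.442/0.908 = 49% |

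For T = 3 h and p = 1.25 h, the overstatement is 9% with the next meal at 2.5 h and 28% at 2 h. On 5-minute readings with p = 1.25 h and a 3 h gap, mean excursion 0-4 h goes from 28.3 to 35.2 mg/dL for a 40 mg/dL peak, and from 56.6 to 70.4 mg/dL for an 80 mg/dL peak.

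**Step 4. Average over breakfasts (illustrative).** Breakfast and lunch times were drawn from normal distributions restricted to the SAP windows. The Step 3 formula with p = 1.25 h was then averaged over the resulting gaps.

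| Assumed breakfast (SD) | Assumed lunch (SD) | Lunch within 4 h | Mean iAUC 0-4 h overstated by |
|---|---|---|---|
| 07:00 (1 h) | 12:30 (0.75 h) | about 10% | about 1% |
| 07:30 (1 h) | 12:30 (0.75 h) | about 20% | about 3% |
| 08:00 (1.25 h) | 12:30 (1 h) | about 34% | about 8% |
| 09:00 (1.25 h) | 12:30 (1 h) | about 58% | about 18% |

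An earlier peak raises these a little (about 9% in the third row with p = 1.0 h).

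**The case against.** The strongest reply concerns weight. iAUC and mean excursion are in neither the Protocol's nor the SAP's table of objectives and endpoints. They fall under SAP 6.9.3, which treats CGM outcomes outside the primary and secondary sets as exploratory. The post-meal endpoints that are in those tables, highest PPG and time to it, already have a next-meal exclusion. This stands, and it sets the severity.

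A second reply is that the same derivation is applied at Visit 3 and Visit 14 in the same participants. The Protocol (5.3.1) also asks for three regular main meals and no major change in diet. A reader might infer from the single-meal percentages that change from baseline is biased by a similar amount. The documents do not support that. The percentages describe the level of a value; with similar spacing and a similar next-meal response much of this cancels in the change, and nothing in the plan is shown to alter spacing.

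A reader might also take one meal-time scenario as the expected effect, or suppose that all by-meal values are affected. The meal times are assumed, so only the range can be reported, and dinner is outside the problem. Nor is the direction certain: iAUC is a net area, so next-meal readings below the starting glucose would lower it.

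None of this supplies the missing rule. Footnote c cannot be stretched to cover it, because its wording is confined to time in ranges.

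**Conclusion.** The omission is certain from the text. Followed literally, SAP 9.3 and 9.4 count the next meal's glucose as the earlier meal's response whenever that meal starts before T. The reach is limited to breakfast (mainly 0-3 h and 0-4 h), lunch at 0-3 h and 0-4 h, and the across-meal average, on days with a short gap.

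The size is not known. Under the assumed curve it is roughly 7% to 49% of iAUC 0-4 h for a single breakfast or lunch with the next meal at 3.5 to 2.5 h, and about 1% to 18% averaged over breakfasts, usually upward. Both ranges rest on assumed curves and the second also on assumed meal times. Change from baseline is distorted only to the extent that spacing or the next-meal response differs between lead-in and maintenance.

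It would be tempting to read this as undermining the study's post-meal or time-in-range conclusions. It does not: the 24-hour primary endpoint, the ICR and dose endpoints, and highest PPG do not use these derivations. Severity: minor.

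**What to change.** Add one sentence to each of SAP 9.3 and 9.4: a meal on a given day contributes to iAUC 0-T and mean excursion 0-T only if no next meal event is recorded before T.

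- Exclude that meal interval, not the patient. The wording of 9.8 should not be copied, because it speaks of data from patients and leaves the unit of exclusion unclear.
- Do not truncate as footnote c does. Truncation would give iAUC values summed over unequal lengths.
- Define the next meal event from the CGM-app meal entries and say whether snack entries count. Snacks are allowed, but the Protocol (4.1.1) requires app entries only for breakfast, lunch and dinner.
- Report the number of contributing meals at Visit 3 and Visit 14, by meal and window.
- In the same edit, reconcile footnote d (difference at a time point) with 9.4 (average over the interval).

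The cost is a few sentences of SAP text and fewer meals behind the 0-3 h and 0-4 h values. Meals with short gaps are left out, so those results describe the better-spaced meals; the counts would make that visible.
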